The study is a minimal risk study, with all subjects receiving the arch supports being investigated. There is no placebo offered. Initial evaluation of all subjects will include all imaging and measurements. Collection of subjective responses will occur after 4 weeks, 8 weeks, and 12 weeks of treatment.

4. Subject Selection

A total of 50 subjects will be enrolled. Subjects must meet the following inclusion and exclusion criteria:

Inclusion

1. Men or women ≥ 18 and ≤ 65 years of age

2. The subject is able and willing to comply with study procedures and a signed and dated informed consent is obtained
3. Subjects diagnosed with symptomatic hallux valgus and/or plantar fasciitis and/or metatarsalgia.
4. Patient has had foot pain for at least 30 days.
5. Willing and able to utilize insole when walking for 90 days.
6. BMI \leq 35
7. Able to walk up to 0.5 miles without difficulty, in a 24-hour period.

Exclusion

1. Inability or unwillingness to comply with study procedures
2. Gross asymmetry in feet, where shoe size differs by 2 or more full sizes between right and left foot
3. Subject has had a CT performed within the last 30 days, for any body part.
4. Prior partial or total amputation of a foot
5. BMI $<$ 35.
6. Unilateral or bilateral foot deformity that would hinder the fitting of an over-the-counter arch support, such as active Charcot foot or Charcot with boney prominence
7. Ulcers or open sores on either foot
8. Currently wearing custom shoes or insoles.
9. Currently ambulating with a cane, crutches, walker.
10. Currently using any type of foot or ankle brace, and/or having used a brace in the last 30 days.
11. Pregnancy

Subject Recruitment:

Subjects will be recruited from the clinicians in the Division of Podiatry under the Department of Orthopaedics. Additionally, the sponsor, Good Feet Worldwide has a trade store the MGH service area, and will allow us to promote the study at their location with an advertisement poster. Potential subjects from the trade store will be referred to our clinics for screening and, when appropriate, recruited for the study.

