6. STUDY PROCEDURES

Table 1: Schedule of Visit Activities

Study Procedures	Screening and Treatment	Follow-up Visits (Every 28±3 days)			
		Week 0	Week 4	Week 8	Week 12
		Visit 1	Visit 2	Visit 3	Visit 4
Informed Consent	X				
Inclusion/Exclusion Criteria	X				
Medical History and Demography	X				
Urine Pregnancy test for women	X				
Physical Exam (incl Ht & Wt)	X	X	X	X	
Selection and fitting of insoles	X				
Clinical assessment of Foot Function	X	X	X	X	
Weightbearing CT w & w/o insoles	X				
Weightbearing X-ray w & w/o insoles	X				
Administer VAS, OFS exam	X	X	X	X	
Review Diary		X	X	X	
Schedule subsequent visits	X	X	X		
Record Adverse Events		X	X	X	

a. Screening / Baseline – Visit 1 (Day 1)

Informed consent must be obtained from each subject before any study procedure can commence. The consent form will be given on an IPad via RedCap signed on paper. The subject will sign and date the Informed Consent Form and undergo the following evaluations/procedures:

Medical History and Physical Assessment

- Determination of eligibility based on inclusion/ exclusion criteria
 - Urine pregnancy test for all women. Pregnant women are not eligible to participate.
- Demographics (date of birth, gender, race) will be recorded
- Medical history: relevant medical history, including history of current disease, and information regarding underlying diseases will be recorded.
- Physical exam will be performed and results recorded
- Height and weight will be measured and recorded.
 - Calculate subject's Body Mass Index

Foot Assessment

- Clinical evaluation of feet will be performed by Podiatrist Study Investigator
 - Classification of foot type
 - Pathologies and painful conditions will be identified
 - Additional ancillary conditions will be included in the history
 - Back, Knee, and Ankle pain along with associated diagnoses and prior treatments
 - Dermatologic conditions
 - Neurovascular measurements
 - Assessment of standard shoe gear
 - Generalized foot appearance (i.e. edema, tender areas, etc.)
 - Basic gait assessment

Subjective Pre-Treatment Assessment:

- VAS (Visual Analog Scale) and OFS (Orthopedic Foot Score) data collected to determine pre-treatment levels of pain and function. The following validated questionnaires will be completed by each study subject.
 - ACFAS Universal foot Evaluation
 - AOFAS Outcome score
 - Oswestry Low Back Disability score
 - Pain Intensity Score
 - Global Health Test
 - Pain Interference

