- Pre-treatment assessment to be completed on day one.
- Subjects will describe their immediate impressions without and with the arch support in place.

Insole Selection

- Based on clinical assessment, properly sized set of arch supports and properly fitted athletic shoes will be dispensed to the study subject. Fit and comfort will be confirmed before proceeding with other data collection steps.

Baseline Measurements

- Each subject will have one weight bearing CT and one weight bearing X-ray series (AP/Lateral) taken barefooted and a second series taken with the selected arch support in place. Subjects are enrolled sequentially, and there is no placebo group.
- Image analysis will compare position and alignment of bones of the foot to measure differences in positioning with and without arch supports, using CT and X-ray. X-ray measurements will include intermetatarsal angles, hallux abductus angle, sesamoid position, metatarsal declination angle, calcaneal inclination angle, talocalcaneal angle, calcaneocuboid angle, and overall morphology. CT measurements will be used to determine the 3-dimensional positioning of the foot bones, and will document the change in position that occurs with and without arch support.

Logging of Activities and Symptoms

- Study subjects will be issued a diary and they are to record the following data on a weekly basis. The diary will be sent to the patient via email and RedCap links.
 - Estimated distance walked (Those able to count steps are encouraged to do so.).
 - Activities of Daily Living
 - Symptoms, and level of pain rated on a VAS scale.
 - Compliance with wearing of insoles and athletic shoes

b. Treatment Phase

We will be conducting follow up surveys via email and RedCap links with patients.

Monthly follow up (End of weeks 4, 8, and 12)

- Confirmation of eligibility based on inclusion/ exclusion criteria
- Medical history: New or relevant changes to medical history, including history of current disease, and information regarding underlying diseases will be recorded
- Review of logged data from daily diary
- Completion of physician re-assessment and OAS and VAS scoring.
- Validated questionnaires will be completed at each of the 3 follow-up visits.
 - ACFAS Universal foot Evaluation
 - AOFAS Outcome score
 - Oswestry Low Back Disability score
 - Pain Intensity Score
 - Global Health Test
 - Pain Interference
- Record any Adverse Events

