- Clinical photographs will be taken with and without the arch support in place, while barefooted.

c. Study Completion/Termination

When the subject completes the study, voluntarily withdraws, is withdrawn for any reason, the study is terminated, or the Investigator is no longer able to locate the subject, the reason for the withdrawal will be reported along with any relevant information concerning the device, subject condition or death.

All subjects withdrawn from the study due to an adverse event, or have an adverse device effect or serious adverse event at study completion, will be followed until the adverse device effect or serious adverse event is resolved, a resolution is no longer expected or it returns to baseline.

Treatment Discontinuation

After completing the estimated 12-week visit requirements, the subject will be considered to have completed the study. In all cases of withdrawal, the date and the reason for withdrawal are to be documented.

Primary Endpoint

The primary endpoint is the change in symptoms when arch supports are worn, as compared to baseline. Change in symptoms and relief of pain will be quantified based on subjective completion of validated questionnaires. Data from the questionnaires will provide a reliable assessment of symptomatic relief from the foot ailments being evaluated.

Secondary Endpoint

The secondary endpoint is the change in foot morphology when shoe inserts are worn. The change to be documented is the acute change that occurs in the boney structure of the foot when it is supported with the orthosis. A critical part of the analysis is to demonstrate if there are measurable changes in foot morphology when supported, and to determine if those changes correlate with symptomatic changes in the study subject's foot condition.

Remuneration

Study subjects will not be paid to participate in this study. However, all participants will receive new orthoses and new shoes, and will be permitted to keep these items at the conclusion of the study. Also, all study participants will receive up to \$50 to reimburse them for any travel expenses related to the study. We would like to pay the participants by check on the date of their visit, if permitted to do so.

Sharing of Data and Confidentiality

All data will be kept within the confines of MGH. Since there are no other sites involved in the study, no outside investigators will have a need for access to the data.

7. Risks and Discomforts

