The risks include discomfort during walking and/or standing, and can include bruise and/or blister formation, exacerbation of existing foot pain, tightness in shoes, temporary foot or leg cramps, bruising of the foot. X-rays and CT scans will be taken, and these tests involve very low levels of radiation. All of the devices being used in this study are currently available for purchase without a prescription, and are being used in the manner in which they were intended.

There are no new applications being explored for either the insoles or shoes that the study subjects will receive during this study. There are no unusual or excessive risks to study subjects, and all procedures being performed on subjects are already in use for diagnostic and treatment purposes.

8. Benefits

Historically, when these conditions (plantar fasciitis, hallux valgus, metatarsalgia) are treated with arch supports, they have responded with significantly less pain, and in many cases, helped the subjects to avoid surgical correction. We expect that the subjects who participate in this study will show signs of improvement in symptoms. They will also benefit from a highly focused medical examination of their

feet. Future patients will benefit from this study by knowing that arch supports are a safe and effective treatment for these foot ailments. The study may also help to optimize arch support design in the future.

9. Statistical Analysis

Statistical plan is for a one-way repeated measures ANOVA to compare the parameters with participants with and without arch-support insoles for each slope. We anticipate using SPSS for Windows (SPSS Science Inc., Chicago, IL, USA) for the statistical analyses. Levene's test will be used to test the homogeneity of the variances. A Kolmogorov-Smirnov test will be used to evaluate the normality of the data, a Wilcoxon test will be used when the data are not normally distributed. The significance level was set at $\alpha = 0.05$. The effect size (ES) for the difference from baseline will be calculated for each variable as a measure of the practical relevance of the significance using Cohen's d ; ES values between 0.20 and 0.49 are considered small, those between 0.50 and 0.79 are considered moderate, and those 0.80 and above are considered large.

10. Monitoring and Quality Assurance

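### Section 9 gives no runnable test of the primary endpoint: its one main test refers to slopes the study does not have, and neither the questionnaire nor the follow-up visit is fixed

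*Combined protocol and SAP*

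**What the plan says.** **Primary endpoint (Section 6, Primary Endpoint).** "The primary endpoint is the change in symptoms when arch supports are worn, as compared to baseline". On measurement: "Change in symptoms and relief of pain will be quantified based on subjective completion of validated questionnaires". No instrument or visit is named.

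**Instruments (Section 6, Subjective Pre-Treatment Assessment).** "The following validated questionnaires will be completed by each study subject". Six follow: ACFAS, AOFAS, Oswestry, Pain Intensity, Global Health and Pain Interference. VAS and OFS are also mentioned. It is unclear whether they are further instruments or umbrella labels for the six.

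**Timing.** Baseline is Day 1. Section 3 adds: "Collection of subjective responses will occur after 4 weeks, 8 weeks, and 12 weeks of treatment". Section 6, Treatment Phase, agrees: "Validated questionnaires will be completed at each of the 3 follow-up visits".

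**Imaging (Section 6, Baseline Measurements).** "Image analysis will compare position and alignment of bones of the foot to measure differences in positioning with and without arch supports". This is done at Visit 1 and serves the secondary endpoint.

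**Analysis (Section 9).** The main test is a "one-way repeated measures ANOVA to compare the parameters with participants with and without arch-support insoles for each slope". Levene's test is to check variances, a Kolmogorov-Smirnov test is to check normality, and an unspecified Wilcoxon test is the fallback. Alpha is 0.05, with no sidedness or multiplicity rule. Also: "The effect size (ES) for the difference from baseline will be calculated for each variable".

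**The concern.** Section 9 never mentions symptoms, questionnaires, the primary endpoint, a week or a visit. Its one main test is conditioned on slopes, and nothing elsewhere in the protocol describes a slope or incline. This is more than missing detail, because the one test that is written down does not fit the study.

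The primary analysis is therefore open to choice after the data are known. A four-visit overall test, baseline against one visit, baseline against each visit, and baseline against the mean of the follow-up visits could all be presented as the planned analysis. They answer different questions. The overall test, for instance, can reject because any two visits differ. The choice changes the false-positive rate and, when the benefit is not constant over time, it can change the conclusion. With no control arm, a test fixed in advance is the main safeguard against selective reporting of the primary result.

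**Working it through.** **1. Can the sentence be matched to the design?**
- Slope: no counterpart in the procedures, the schedule of visits or the endpoints.
- With and without insoles: a paired measurement of this kind is specified for CT and X-ray at Visit 1. Otherwise there are only immediate impressions and photographs.
- With only two conditions, a one-way repeated measures ANOVA is equivalent to a paired t-test. It does not describe an analysis of questionnaires at weeks 0, 4, 8 and 12.

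**2. Do the supporting rules settle it?** No.
- Levene's test compares variances of independent groups, and this study makes single-arm, within-subject comparisons.
- A four-visit ANOVA relies on sphericity, which is not addressed.
- A paired Wilcoxon test covers two occasions only, so a four-visit plan would have no fallback for non-normal data.

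**3. How many candidate tests are open?** 6 questionnaires × 3 visits = 18. If VAS and OFS are separate instruments, 8 × 3 = 24.

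**4. False positives when nothing changes.** If the tests were independent, the chance of at least one p < 0.05 is 1 − 0.95^k:
- k = 3: 1 − 0.95³ = 14.3%
- k = 18: 1 − 0.95¹⁸ = 60.3%

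The tests share a baseline and are correlated, so these figures overstate the chance, and simulation is needed. Only n = 50 comes from the protocol. Every correlation and effect below is assumed, because the documents give none.

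Model for one questionnaire: four visits, multivariate normal, unit SD, no missing data. The baseline–follow-up correlation r_b is 0.3 to 0.6 and the follow-up–follow-up correlation r_f is 0.6 to 0.9, giving 16 cells. The tests are:
- overall F on 3 and (50 − 1) × 3 = 147 degrees of freedom;
- t = mean change ÷ (SD of change ÷ √50) on 49 degrees of freedom, at each visit.

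Two changes from the same baseline correlate at (1 + r_f − 2r_b) ÷ [2(1 − r_b)], which drives the any-visit rate:

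| r_b / r_f | Correlation of changes | Any of 3 visits | Uncorrected F |
|---|---|---|---|
| 0.6 / 0.6 | 0.4 ÷ 0.8 = 0.50 | 12.4% | 4.9% |
| 0.5 / 0.8 | 0.8 ÷ 1.0 = 0.80 | 9.8% | 6.5% |
| 0.3 / 0.9 | 1.3 ÷ 1.4 = 0.93 | 7.9% | 8.9% |

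Over all 16 cells:
- any visit: about 8% to 12% (false improvement alone 4.0% to 6.1%, against a nominal 2.5%);
- uncorrected F: about 5% to 9% (median 6.2%);
- F with Greenhouse-Geisser correction: 4.6% to 5.0%;
- one fixed visit: about 5%.

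For all 18 tests, with a between-visit correlation of 0.5, the rate is about 26% when the questionnaires correlate at 0.9 and about 55% when they are uncorrelated.

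**5. Do the readings disagree when there is an effect?** Chance of p < 0.05 on one questionnaire:

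| Assumed change at weeks 4 / 8 / 12 (SD) | Uncorrected F | Any visit | Week 12 only |
|---|---|---|---|
| 0.4 / 0.2 / 0, full grid | 75% to 99% | 67% to 90% | 5% |
| 0.2 / 0.1 / 0, full grid | 22% to 45% | 25% to 41% | 5% |
| 0.3 / 0.3 / 0.3, the three cells above | 55% to 67% | 52% to 87% | 42% to 65% |

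**6. What one fixed test would give.** The plan shows no derivation for its 50 subjects, so there is no figure to reproduce. For one two-sided paired test at 0.05, the detectable standardised change at 80% power is (1.960 + 0.842) ÷ √50 = 0.40. Power at d = 0.50, the lower limit of what Section 9 calls moderate, is about 93%.

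**The case against.** The best defence is that week 0 is the without-insole condition and follow-up the with-insole condition. The endpoint is defined against baseline, and Section 9 plans Cohen's d for the difference from baseline. Part of this stands. A reader might infer that no contrast is defined at all, and that goes too far, because the reference point is fixed. What remains open on this reading is the questionnaire, the follow-up visit or summary, and multiplicity. Cohen's d for each variable is an effect size, not a test.

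Three further limits also stand:
- A reader might infer that a fading benefit would usually be significant under some readings and not under others. That holds at 0.4/0.2/0 SD. At half that size neither the F-test nor the any-visit rule reaches 50%, and with a steady benefit the readings diverge far less.
- Sphericity inflation is modest in most cells. Its maximum needs the extreme 0.3/0.9 cell. The larger exposure is the open choice of questionnaire.
- Counting eight instruments is not secure, because VAS and OFS may be labels for the six listed. The main figures therefore use six.

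Nothing in the documents shows an intention to select a favourable result. The point is that the plan does not prevent it.

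**Conclusion.** The concern holds and should be fixed before outcome data are analysed. Confidence is high on the text: the slope condition does not exist, the with/without measurement matches the secondary endpoint, and no primary questionnaire or visit is fixed.

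The size is illustrative. If the test is left open, the chance of at least one nominally significant primary result under no change rises from 5% to roughly 8% to 12% over three visits on one questionnaire, and to roughly 26% to 55% over six questionnaires at three visits. These figures rest on normal data, complete follow-up and assumed correlations, and the effect scenarios are also assumed. No figure stated in the protocol is contradicted.

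**What to change.** Replace the first sentence of Section 9 with two separate statements.

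- **Primary endpoint.** Name one questionnaire and one change-from-baseline contrast: a single visit such as week 12, or a stated summary of the follow-up visits. The investigators choose and justify both. Test it within subject at two-sided 0.05 with a 95% confidence interval, by a paired test or a mixed model. Either closes the gap if fixed in advance. Make all other questionnaires and visits secondary.
- **Secondary endpoint.** State the with-minus-without imaging comparison at Visit 1 as a paired analysis.

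Then delete the slope reference and Levene's test. If a four-visit F-test is kept, add a sphericity correction. Specify that the Wilcoxon test is the signed-rank test, for two-occasion differences only.

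The cost is wording and a little analysis work, with no new data or subjects. The real price is commitment: a benefit seen only on another questionnaire, or outside the chosen contrast, becomes a secondary result.

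### A normality test on the trial's own data decides whether the four-visit symptom analysis becomes a two-occasion Wilcoxon test with no visit pair named

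*Combined protocol and SAP*

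**What the plan says.** Section 9 (Statistical Analysis) is the only analysis text. The main test is worded as: "Statistical plan is for a one-way repeated measures ANOVA to compare the parameters with participants with and without arch-support insoles for each slope". Then: "A Kolmogorov-Smirnov test will be used to evaluate the normality of the data", and "a Wilcoxon test will be used when the data are not normally distributed". The significance level is 0.05, and Cohen's d is to be calculated relative to baseline.

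Section 6 (Primary Endpoint) states: "The primary endpoint is the change in symptoms when arch supports are worn, as compared to baseline". It names no lead scale and no time point. Section 3 gives the follow-up times: "Collection of subjective responses will occur after 4 weeks, 8 weeks, and 12 weeks of treatment". Section 6b adds: "Validated questionnaires will be completed at each of the 3 follow-up visits". The same six questionnaires and the VAS are also collected before treatment (Section 6a and Table 1), so each symptom scale has four occasions. Imaging is taken once, at Visit 1, with and without the insole. Section 4 sets the size: "A total of 50 subjects will be enrolled".

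Section 9 does not state:
- which form of K-S is meant, or at what cut-off;
- whether raw scores, changes or residuals are tested;
- whether the switch is made per scale or per visit;
- which Wilcoxon test is meant, and which occasions it compares;
- any adjustment for several comparisons.

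**The concern.** A fallback test should answer the same question as the test it replaces. For imaging it does: there are two conditions, and a paired Wilcoxon test fits. For symptoms, a one-way repeated measures ANOVA over the four occasions asks whether the mean differs at any of them. A Wilcoxon test asks about two of them. The rank counterpart for four related occasions is Friedman, which Section 9 does not mention. Failing the gate therefore changes the hypothesis as well as the distributional assumption, and the reader cannot tell which pair or pairs will be reported.

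The gate is also a poor instrument for this choice. Plain K-S treats the mean and SD as known. When both are estimated from the sample it almost never rejects, whereas the Lilliefors form corrects for the estimation. Coarsely scored questionnaires then push the two forms towards opposite answers, so two analysts could both follow Section 9 and report different tests of the primary endpoint. In a single-arm study with six questionnaires plus a VAS, that leaves a positive result open to challenge.

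**Working it through.** The plan gives no power, SD or sample-size derivation, so there is no stated figure to reproduce.

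**Inputs from the protocol:** n = 50 (Section 4); alpha 0.05 (Section 9; two-sided assumed); four symptom occasions (Sections 3 and 6).

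**Assumptions, not in the protocol:** normally distributed underlying score with mean 5 and SD 2 (range 1.5 to 2.5) on a 0-10 scale, rounded in steps of 0.1 to 2; equal correlation between visits of 0.3 to 0.7.

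**1. Threshold of the gate.** D = max |F_n(x) - Φ((x - mean)/s)|. The 5% critical value at n = 50 is 0.188 for plain K-S and 0.125 for Lilliefors.

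**2. What rounding alone contributes.** With whole-number scores, the share at the central value is Φ(0.5/2) - Φ(-0.5/2) = 2 × 0.0987 = 0.197. Half of that step, about 0.099, is built into D before any sampling noise. That is close to 0.125 and well short of 0.188. With 0.1 steps the same term is Φ(0.05/2) - 0.5 = 0.010, which is negligible against either threshold.

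**3. Simulated flagging rate for one visit, SD 2.**

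| Score step | Plain K-S | Lilliefors |
|---|---|---|
| 0.1 | 0.03% | 4.5% |
| 0.5 | 0.2% | 23% |
| 1 | 5.7% | 81% |
| 2 | 87% | 100% |

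For 1-point steps, as the SD goes from 2.5 down to 1.5, plain K-S runs from 1.8% to 22.5% and Lilliefors from 56% to 98.5%. If one flagged visit out of four triggers the switch (correlation 0.5), the rates are 20% against 99.9% for whole numbers, and the two forms choose different branches in about 80% of trials. With 0.1 steps they are 0% against 17.8%; the latter is close to 1 - 0.95^4 = 18.5%, which four independent 5% tests would give on normal data.

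**4. Consequence of changing the hypothesis** (whole-number scores, SD 2, correlation 0.5).
- True change of -0.8, -0.4 and 0 at weeks 4, 8 and 12: the four-visit ANOVA rejects in 77% of trials. Wilcoxon against baseline rejects in 77%, 27% or 5%, depending on whether week 4, 8 or 12 is picked. ANOVA and the week 12 Wilcoxon disagree in 73%.
- Constant change of -0.6: they disagree in 23%.
- No change (correlation 0.3 to 0.7): they disagree in about 6-7%.

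**5. Error rates with no true change.**
- ANOVA over four visits: 4.8-5.1%. Friedman: 4.8-5.3%.
- One pre-named baseline to week 12 Wilcoxon: 4.3-5.3%.
- K-S gate followed by paired t or Wilcoxon on that one pair: 4.5-5.1% across whole-number, floor-limited and skewed scores in one set of runs; no more than about 6% in another.
- Any of three unadjusted Wilcoxon tests against baseline: 11.6-12.7% over correlations 0.3 to 0.7 (independence: 1 - 0.95^3 = 14.3%). In a direct comparison at correlation 0.6, Wilcoxon gave 12.8% and paired t 13.3%; a repeat gave 14.4% for both.

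**6. Is the gate needed?** The paired t test on whole-number scores piled at the floor kept 4.8-5.2% error at n = 50. The repeated measures ANOVA without a sphericity correction drifted to 5.6-5.9% when correlation decayed at 0.6 per visit. That drift is small, and a standard correction addresses it.

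**The case against.** The strongest reply is that the rule is written in advance and does little harm to error control. Much of this stands. A reader might infer that the gate itself inflates false positives; the gated two-occasion procedure stays near 5-6%, so it does not. The 80% is a rate of flagging non-normality under an assumed scale. It is not a rate of wrong conclusions, and the protocol does not state the scoring steps. The 12-14% belongs to running three unadjusted comparisons, whichever test is used, and Section 9 does not say that any one of them would count as success.

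A reader might go further and count all six visit pairs, at about 20-21%. The protocol describes no such procedure: the endpoint and the effect sizes both refer to baseline. Nor does a higher Wilcoxon rejection rate for a skewed change with mean zero (16-17% against 6% for the t test) show false positives. That situation is not null for the signed-rank test, so the figures show only that the two tests address different quantities.

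It is also fair that Section 9 never names visit as the ANOVA factor, and that its wording of with and without insoles suits imaging. The lead scale and time point are undefined more generally. That is a reason to settle them in the same edit. It does not rescue a two-occasion fallback for data with four occasions, and a rule written in advance must still lead to one analysis. This one does not.

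**Conclusion.** The point holds for the primary symptom endpoint and is worth correcting before any analysis. It does not hold for the imaging, where a paired Wilcoxon matches in form. The mismatch between four occasions and a two-occasion fallback follows from the text alone and needs no simulation.

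The size of the gate's instability does rest on assumptions. With whole-number 0-10 scores, mean 5 and SD 2, the choice of K-S form moves flagging from about 5% to about 80% of visits; with fine scoring the gap is about 0% against 5%. The direction held over every SD and rounding step tried, but the exact percentages are illustrative. The transient-change example shows how far the two branches can part and is not a forecast for this device.

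The defect is an undetermined hypothesis for the primary endpoint. The documents do not support a claim that the normality gate by itself raises the type I error. A multiplicity cost of about 12-14% arises only if three baseline comparisons are run unadjusted and any one is counted as success.

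**What to change.** In Section 9, delete the K-S gate and state, whatever the distributions look like:

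1. Within-person change from baseline is analysed with a mean-based repeated measures model across the four visits, with a sphericity correction such as Greenhouse-Geisser.
2. One baseline contrast, for example week 12, is named in advance as primary; the other visit contrasts are adjusted for multiplicity.
3. With/without-insole imaging is analysed with a paired t test.
4. A Wilcoxon signed-rank test of the same named change is reported as a sensitivity analysis only. If a rank test over all four visits is wanted, it is Friedman.

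Naming the lead symptom scale in the same edit would make the primary contrast complete. The cost is two or three sentences in Section 9, one sensitivity line per outcome, and slightly stricter secondary visit contrasts. No new visits or data are needed.
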